**Table 2. Early Termination Schedule of Activitiesa**

Protocol Activities	As soon as possible after determining subject will be discontinued from study	Early Termination Visit 1	Early Termination Telephone Contact 1	Early Termination Visit 2	Early Termination Telephone Contact 2	Early Termination Visit 3
		~8 Weeks after last SC dose	~12 Weeks after last SC dose	~16 Weeks after last SC dose	~20 Weeks after last SC dose	~24 Weeks after last SC dose
X-rays of major joints and any other at risk joints b	X					X
General Physical Examination		X				X
Musculoskeletal Physical Examination		X Japan only		X Japan only		X Japan only
CCI						
Vital Signs (BP, HR)		X		X		X
Orthostatic Blood Pressure (supine/standing)		X				X
Body Weight		X				X
ECG 12-lead		X				X
ECOG Performance Score		X				X
Subject Reported Assessments Completed at Study Visits						
CCI						
OR-SDS e		X				
PGA of Cancer Pain		X				
CCI						
CCI						
Laboratory						
Serum Pregnancy Test		X		X		X c
Hematology				X		X
Blood Chemistry				X		X
PT/PTT				X		X
Serum and Plasma Retention Samples		X		X		
CCI						

Protocol Activities	As soon as possible after determining subject will be discontinued from study	Early Termination Visit 1	Early Termination Telephone Contact 1	Early Termination Visit 2	Early Termination Telephone Contact 2	Early Termination Visit 3	
		~8 Weeks after last SC dose	~12 Weeks after last SC dose	~16 Weeks after last SC dose	~20 Weeks after last SC dose	~24 Weeks after last SC dose	
Serum ADA		X		X		X	
CCI							
Subject Weekly Assessments (IRT subject diary)d							
Assessment of Cancer Pain (NRS)	-----X-----						
Opioid use	-----X-----						
Joint Pain Assessment	-----X-----						
NSAID use	-----X-----						
Other Assessments/Procedures Conducted at Study Visits							
Adverse event assessment		X	X	X	X	X	
Review concomitant medication		X	X	X	X	X	
Review subject compliance with IRT (subject diary)		X	X	X	X		
Review IRT (Subject diary) entries		X	X	X	X	X	
Reminder of contraceptive requirements e	X	X	X	X			
Liberalize oral opioid regimen if needed f	-----X-----						
Begin other standard of care treatment (except NSAIDs or intra-articular corticosteroids) if needed f	-----X-----						

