In the event a subject refuses the Early Termination Safety Follow-Up, or chooses to discontinue during the Safety Follow-Up (after Week 24 and through Week 48), a complete Early Termination visit should be performed that should include all procedures described in [Section 6.4.1.1](#) Early Termination 1 (also described in [Table 2](#) column 3), including the x-rays of major joints provided at least 30 days have elapsed since the last x-rays were collected (see [Section 6.4.1](#) and [Table 2](#) column 2). In addition, female subjects will be advised to continue their contraception regimen during a period of 112 days (16 weeks) after the last dose of SC study medication.

**Withdrawal of Consent:** Subjects who request to discontinue study treatment will remain in the study and will continue to be followed for protocol specified follow-up procedures unless they specifically withdraw consent for any further contact with him/her or persons previously authorized by subject to provide this information. Subjects should notify the investigator of the decision to withdraw consent from future follow-up in writing, whenever possible. The withdrawal of consent should be explained in detail in the medical records by the investigator, as to whether the withdrawal is from further treatment with study drug only or also from study procedures and/or post-treatment study follow-up, and entered on the appropriate CRF page. If the subject withdraws from the study, and also withdraws consent for disclosure of future information, no further evaluations should be performed, and no additional data should be collected. Pfizer may retain and continue to use any data collected before such withdrawal of consent.

**Lost to Follow-Up:** All reasonable efforts must be made to locate subjects as to determine and report their ongoing status. This includes follow-up with persons authorized by the subject as noted above. Lost to Follow-Up is defined by the inability to reach the subject after a minimum of three documented contacts (via phone calls, faxes, and/or emails) as well as lack of response by subject to one registered mail letter. All attempts should be

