#### **6.4.1.1. Early Termination Visit 1 (~8 Weeks after Last Dose of SC Study Medication)**

Refer to the Early Termination Schedule of Activities [Table 2](#) and [Section 7](#) for information on the procedures to be performed at Early Termination Visit 1.

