#### 7.3.4. Laboratory Safety Assessments

Blood and urine tests for safety assessments and/or determination of eligibility will be performed as indicated in this table and described in the subsections below:

Chemistry	Hematology	Other	Urinalysis
Screening, Baseline, Weeks 16, 32 and 48 (or Early Termination):	Screening, Baseline, Weeks 16, 32 and 48 (or Early Termination):	Screening only: Hemoglobin A1c Serum FSH, if	Screening only (urine macro panel):

Chemistry	Hematology	Other	Urinalysis
Sodium, potassium, chloride, bicarbonate, glucose (non-fasting), Blood Urea Nitrogen (BUN), creatinine, calcium, phosphorus, magnesium, total and direct bilirubin, total protein, albumin, cholesterol, triglycerides, gamma glutamyltransferase (GGT), alanine aminotransferase (ALT), aspartate aminotransferase (AST), lactic dehydrogenase (LDH), alkaline phosphatase, creatine phosphokinase (CPK), uric acid, prothrombin time (PT), partial thromboplastin time (PTT)	Complete blood count with differential	
applicable
 
Hepatitis screen (eg, HBsAg, Anti-HCV), HIV test (HIV Ab screen)
 
Urine toxicology screen (eg, for opiates, barbiturates, amphetamines, cocaine, propoxyphene, methadone, phencyclidine, and methaqualone).
 
Screening, Week 24, 32 (or Early Termination): Serum Pregnancy Test
 
Baseline, Weeks 8 and 16 (Pre-dose): Urine Pregnancy Test
 
Baseline, Weeks 16, 24 and 32: Serum and plasma retention samples
	
pH, protein, glucose, ketones, blood, bilirubin, nitrite, specific gravity and leukocytes.
 
Microscopic analysis performed if abnormalities are present on the above components. If urine protein by dipstick is <math>\geq 2+</math>, then 24-hour urine collection is required for 24-hour urinary protein assessment

Table does not include CCI [REDACTED] ADA CCI [REDACTED]; (Refer to sections below for collection details).			

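### The single exit visit for subjects who refuse follow-up carries no hematology, chemistry or PT/PTT, although Section 7.3.4 lists these tests at Early Termination

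*Protocol*

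**What the plan says.** Section 6.4 of the protocol covers two kinds of leaver together. The first is introduced by "In the event a subject refuses the Early Termination Safety Follow-Up"; the second is anyone who stops during Safety Follow-Up, after Week 24. For both, "a complete Early Termination visit should be performed that should include all procedures described in" Section 6.4.1.1, further identified as "Early Termination 1 (also described in" Table 2, column 3. X-rays of the major joints are added if at least 30 days have passed since the last set.

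Section 6.4.1.1 has no list of its own. It sends the reader to Table 2 and Section 7 for "information on the procedures to be performed at Early Termination Visit 1".

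In Table 2 the relevant rows read "Hematology X X" and "Blood Chemistry X X", and the PT/PTT row has the same pattern. In each row the two marks stand under Early Termination Visits 2 and 3, about 16 and 24 weeks after the last dose. The Visit 1 cell is empty.

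Section 7.3.4 gives the timing of chemistry (which there includes PT and PTT) and of hematology as "Screening, Baseline, Weeks 16, 32 and 48 (or Early Termination"). Table 1 schedules the same tests at Screening, Baseline and Weeks 16, 32 and 48.

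**The concern.** The exit visit is called complete, and it is the only Early Termination visit these subjects will have. Its content is copied from a visit without the panel that Section 7.3.4 lists for Early Termination. A site following Section 6.4 and Table 2 draws no panel; a site following Section 7.3.4 does. Both are following the protocol.

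Safety is the secondary objective, and chemistry and hematology are named safety measures in Section 2.2.2.3. A subject with no post-dose panel contributes no post-baseline value to the laboratory summaries. The liver criteria in Section 8.6.2 cannot be checked for that subject from scheduled samples. The subjects concerned are also not a random subset, since they are defined by leaving and declining follow-up.

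**Working it through.** There is no sample size, power or error rate to reproduce here. The check is a cross-reading of the schedules followed by a count.

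**Step 1: what the exit visit contains.** Counting the Table 2 columns: 1 is the activity, 2 the x-rays taken as soon as possible, 3 Early Termination Visit 1, 4 the first telephone contact, 5 Visit 2, 6 the second telephone contact, 7 Visit 3. Section 6.4 points to column 3.

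**Step 2: whether the empty cells are real.** Other rows fall where they should. Vital signs are marked at Visits 1, 2 and 3, the general physical examination at Visits 1 and 3, and retention samples at Visits 1 and 2. The empty Visit 1 cells for hematology, chemistry and PT/PTT are therefore not a shifted column.

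**Step 3: earlier post-dose panels.** In Table 1 the first post-dose hematology, chemistry and PT/PTT are at Week 16 (Day 113). There are none at Weeks 2, 4, 8 or 24. The next are at Weeks 32 and 48.

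**Step 4: count of scheduled post-dose panels**, assuming each due dose was given.

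| Subject | Doses | As written | With the tests at the single exit visit |
|---|---|---|---|
| Leaves before Week 8, refuses follow-up | 1 | 0 | 0 + 1 = 1 |
| Leaves after the Week 8 dose and before Week 16, refuses | 2 | 0 | 0 + 1 = 1 |
| Leaves after the Week 16 visit and before Week 32, single exit visit | 3 | 1 (Week 16) | 1 + 1 = 2 |
| Leaves after Week 32 and before Week 48, single exit visit | 3 | 2 (Weeks 16, 32) | 2 + 1 = 3 |
| Leaves before Week 16, accepts follow-up | 1 or 2 | 2 (Visits 2, 3) | 2 (unchanged) |

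**Step 5: exceptions.** Under Section 7.4.6, subjects discontinued into the joint-replacement substudy have all Week 24 and Week 48 procedures at the discontinuation visit. The Week 48 column of Table 1 includes these tests, so they are covered. Under Section 6.4, no further evaluation is made in subjects who also withdraw consent for disclosure of future information, so no schedule reaches them.

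**The case against.** The strongest reply is that nothing conflicts. The Early Termination entry in Section 7.3.4 names no visit, and Section 7.3.4.1 refers blood testing to Tables 1 and 2, which place it at Visits 2 and 3. The early-termination schedule is also a coherent copy of the main one. Visit 1 is about 8 weeks after the last dose, as Week 24 is (24 − 16 = 8), and Visit 2 about 16 weeks after, as Week 32 is (32 − 16 = 16). Table 1 has no panel at Week 24 and has one at Week 32. Pregnancy tests in Section 7.3.4.3 pair the visits in the same way.

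All of that stands for subjects who accept follow-up: Visits 2 and 3 give them the tests, and Section 7.3.4 is met. It does not help a subject whose only Early Termination visit is a copy of Visit 1.

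Three stronger readings might be inferred, and the documents do not support them:

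- **That compliant early terminators are tested too late.** A completer also goes from the last dose at Week 16 to the next panel at Week 32, the same 16 weeks. Wanting an earlier sample is a preference about frequency, not an inconsistency in the plan.
- **That the suspension rules would be undercounted.** Section 9.7.1.1 counts serious adverse events as reported, and Section 9.7.1.2 counts reported Hy's Law events across all ongoing tanezumab studies. Serious event reporting for subjects who refuse follow-up runs to 112 days after the last dose (Section 8.2).
- **That a particular number per arm is affected.** The protocol gives neither an early-departure rate nor a refusal rate.

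Unplanned visits are also allowed where needed for a subject's well-being, so the gap is in scheduled results. A sample may still be taken at the investigator's discretion.

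**Conclusion.** The point holds in a narrow form. For subjects whose departure is handled by the single exit visit, Sections 6.4 and 7.3.4 and Table 2 do not agree. The clearest consequence is for a subject who refuses follow-up and leaves before Week 16: zero scheduled post-dose safety panels after one or two doses, against two for the same subject accepting follow-up. Those who leave later through the same visit have one or two earlier panels but none at exit.

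The conclusion rests on reading the complete visit of Section 6.4 as limited to column 3 of Table 2 plus x-rays, which is what the section says. It needs no assumption about departure rates, and the number affected cannot be derived from the protocol. It is worth correcting because the data belong to a stated safety measure and the correction is small. It is not a criticism of the laboratory schedule for subjects who stay or who accept follow-up.

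**What to change.** Reconcile Section 6.4, Table 2 and Section 7.3.4 with one clause in Section 6.4, or a footnote to Table 2: for a subject who refuses Early Termination follow-up or leaves during Safety Follow-Up, the single exit visit also includes the hematology, chemistry and PT/PTT that Section 7.3.4 lists for Early Termination. The Visit 1 column can stay as it is for subjects who accept follow-up.

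Table 2 already has blood drawn at Visit 1 for anti-drug antibody and retention samples, so no new procedure or visit is needed. The cost is one extra set of laboratory tubes, and its analysis, for these subjects only. Subjects who withdraw consent for further data remain without a result, and the clause cannot change that.

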#### Brief summary of procedures for subjects discontinuing from study treatment

X-rays of the knee, shoulder and hip (and any other joint imaged at Screening or identified as at risk during the study) should be performed as soon as possible after the decision to withdraw from the study has been made, provided at least 30 days have passed since the last set of x-rays were collected (refer to [Section 6.4.1](#)).

The remainder of efficacy and safety assessments should be done at the scheduled first visit which is to occur approximately 8 weeks after the last dose of SC study treatment (refer to [Section 6.4.1.1](#), Early Termination Visit 1). The site should also schedule the subject for two additional clinic visits. The second visit should be scheduled to occur approximately 16 weeks after the subject's last dose of SC study treatment (corresponding to more than 5 times the elimination half-life of tanezumab) to collect safety and efficacy data (refer to [Section 6.4.1.3](#), Early Termination Visit 2). Once the clinic visit 16-weeks after the last administration of SC study treatment has been completed and final efficacy assessments have been collected, standard of care analgesia with NSAIDs or intra-articular corticosteroids may be offered to subjects who are completing the remaining 8 weeks of the required follow-up period. The third and final clinic visit should be scheduled to take place approximately 24-weeks after the subject received the last dose of SC study treatment (refer to [Section 6.4.1.4](#), Early Termination Visit 3). Telephone contact will be made with subjects at approximately 12 and 20 weeks following the last SC dose of study treatment. Every effort should be made to have the subject agree to complete the entire 24-week Early Termination Safety Follow-Up described in [Section 6.4.1](#).

Subjects entered in the Early Termination Follow-Up period will be able to take background opioid medication daily up to the Early Termination Follow-Up period Visit 3 (which occurs 24 weeks after the last dose of SC study treatment).

#### **6.4.1. Early Termination Follow-Up Procedures**

As soon as possible following a decision to withdraw a subject from the study is made, provided at least 30 days have passed since the last set of x-rays were collected, x-rays of all joints for which x-rays were obtained at Screening and other at risk joint identified during the study period should be obtained (refer to [Section 7.3.9](#)). X-rays should be submitted to imaging Central Reader.

Refer to the Early Termination Schedule of Activities [Table 2](#).

#### **6.4.1.1. Early Termination Visit 1 (~8 Weeks after Last Dose of SC Study Medication)**

Refer to the Early Termination Schedule of Activities [Table 2](#) and [Section 7](#) for information on the procedures to be performed at Early Termination Visit 1.

#### **6.4.1.2. Early Termination Telephone Contacts 1 and 2 (~12 Weeks and ~20 Weeks after Last Dose of SC Study Medication)**

The subject will be contacted by telephone twice (~12 weeks and ~20 weeks after the last dose of SC study medication) to review adverse events, concomitant medications, compliance with daily/weekly IRT entries and, at Telephone contact 1, to remind female subjects of contraceptive requirements.

Refer to the Early Termination Schedule of Activities [Table 2](#) for the procedures to be performed at the Early Termination Telephone Contacts.

At Telephone Contact 2, schedule x-rays, to occur preferably prior to the Early Termination Visit 3 but if possible, no more than 14 days after the Early Termination Visit 3.

#### **6.4.1.3. Early Termination Visit 2 (~16 Weeks after Last Dose of SC Study Medication)**

Refer to the Early Termination Schedule of Activities [Table 2](#) and [Section 7](#) for information on the procedures to be performed at Early Termination Visit 2.

#### **6.4.1.4. Early Termination Visit 3 (~24 Weeks after Last Dose of SC Study Medication)**

Refer to the Early Termination Schedule of Activities [Table 2](#) and [Section 7](#) for information on the procedures to be performed at Early Termination Visit 3.

### **6.5. Procedures for Subjects Undergoing Joint Replacement**

Subjects who have undergone or plan to undergo total joint replacements or other arthroplasty procedure during the study will be discontinued from study treatment. Follow-up procedures for these subjects are described in [Section 7.4.6](#). In addition, subjects who undergo total knee, hip or shoulder joint replacement surgery during the study (Double-Blind Treatment Period or Safety Follow-Up Period) will be followed for 24 weeks after the procedure as part of a separate substudy, described in [Appendix 16](#), provided the subject consents.

## **7. ASSESSMENTS**

Every effort should be made to ensure that the protocol-required tests and procedures are completed as described. However, it is anticipated that from time to time there may be circumstances, outside of the control of the investigator that may make it unfeasible to perform the test. In these cases the investigator will take all steps necessary to ensure the safety and well-being of the subject. When a protocol-required test cannot be performed, the investigator will document the reason for this and any corrective and preventive actions that he or she has taken to ensure that normal processes are adhered to as soon as possible. The study team will be informed of these incidents in a timely fashion.

## **7.1. Subject IRT Assessments**

The subject IRT assessments described in this section should be completed in the evenings if possible.

### **7.1.1. Daily/Weekly Pain IRT Assessments**

Average pain and worst pain in the index bone metastasis cancer pain site, non-index cancer pain sites and average pain in painful major joints will be assessed by the subject at approximately the same time each day (or each week) with an 11-point Numeric Rating Scale (NRS) ranging from 0 (no pain) to 10 (worst possible pain) captured through IRT. The subjects should describe their pain in the painful site during the past 24 hours by choosing the appropriate number from 0 to 10.

Subjects will record diary entries in an electronic IRT tool. Although the subject is responsible for completing the diary, the site personnel have a number of responsibilities related to the IRT including:

- Assigning, setting up and collecting the IRT devices.
- Instructing subjects on IRT diary use and transmission of data.
- Reviewing subject's IRT (subject diary) during the Screening period (including Baseline Assessment Period) and at each study visit (including phone contact visits) to ensure completeness (eg, by using the IRT vendor's trial manager). Questioning subjects for missing entries and retrain as appropriate. If the issue is technical, work with the subject and/or the IRT vendor to address the problem.
- Reviewing daily and weekly (as applicable) IRT (subject diary) entries.

#### **7.1.1.1. Index Bone Metastasis Cancer Pain Site Assessment**

At Screening, subjects will be asked to identify the most painful site of bone metastasis via IRT. This site will be considered the index bone metastasis cancer pain site. Subjects will be asked to record daily pain ratings for the index bone metastasis cancer pain site as described below.

Average pain and worst pain in the index bone metastasis cancer pain site will be assessed by the subject at Screening and daily during the Pre-Treatment Period to the Week 8 Visit, and then will be assessed weekly using a 24-hour recall period beginning after the Week 8 visit through Week 24 (and weekly during the Early Termination Follow-Up Period, as shown in [Table 2](#)). Refer to [Appendix 9](#) to see examples of the questions the subject will be asked.

#### **7.1.1.2. Non-Index Site(s) of Cancer Pain Assessment**

At Screening, subjects will be asked via the IRT whether they are experiencing cancer pain in site(s) other than the index bone metastasis cancer pain site. If so, they will be prompted to identify up to 2 other site(s), which will be considered a non-index cancer pain site(s). If the subject has more than 2 other painful cancer pain sites, he or she should select the 2 sites which are most painful as the non-index cancer pain sites. Subjects will rate their average

pain and worst pain for each site(s) with an 11-point Numeric Rating Scale ranging from 0 (no pain) to 10 (worst possible pain) during the past 24 hours.

Assessment of pain in non-index site(s) of cancer pain will be performed weekly during the Pre-Treatment Period to the Week 24 Visit (and weekly during the Early Termination Follow-Up Period up to the visit that occurs 16 weeks after the last dose of SC study medication was administered). Refer to [Appendix 9](#) to see examples of the questions the subject will be asked.

#### **7.1.1.3. Joint Pain Assessments**

Pain in each shoulder, hip and knee and any additional major joint that will be imaged at Screening (refer to [Section 7.3.9](#)), will be assessed via IRT at the Screening Visit using the 11-point NRS scale noted below. These joint pain assessments are conducted for joint safety purposes, not for efficacy assessments. Refer to [Appendix 9](#) to see an example of the question the subject will be asked.

Thereafter, on a weekly basis beginning during the Pre-Treatment Period and through Week 48 (or Early Termination as described in [Section 6.4](#)), the subject will also be asked via IRT if he or she experienced new onset or increased pain in any major joint. If a subject responds that he or she has experienced increased pain in a major joint (Post-Baseline), the subject will be asked to rate his/her pain in that joint on the same 11-point numeric rating scale, using a 24-hour recall for the remainder of the study.

A major joint is defined as a mobile synovial joint in the limbs such as shoulders, elbows, wrists, hips, knees, ankles and excluding the joints of the toes and hands.

